5.6 Adverse Event Relatedness

The investigator will be responsible for making a determination on the causal relationship of the AE. Specifically, the investigator will report whether the AE was related to the study procedure or related to the study device.

The causal relationship for each adverse event will be rated as described in *Table 5-1*, below:

Table 5-1: Adverse Event Relatedness

Unrelated	The cause of the AE is known and is not related to any aspect of study participation including the underlying condition.
Possibly Related	There is a reasonable possibility that the event may have been caused by study participation. The AE has a timely relationship to the study procedure(s); however, it follows no known pattern of response and an alternative cause seems more likely or there is significant uncertainty.
Probably Related	It is probable that the event was caused by study participation. The AE has a timely relationship to the study procedure(s) and follows a known pattern of response, but a potential alternative cause may be present.
Definitely Related	The event was definitely related to study participation. A related event has a strong temporal relationship and an alternative cause is unlikely.

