8.7 Medical Risk Analysis

Because the NanoKnife System is investigational within the prostate there may be potential risks and side effects that are unknown at this time. A clinical risk analysis has been prepared which describes the hazards associated with the use of the device and the associated clinical risks associated with the procedure (e.g., general anesthesia) along with the mitigations available to reduce this hazard. Potential risks associated with the use of the NanoKnife System include, but are not limited to, the risk outlined in *Table 8-1*.

Table 8-1: Potential Hazards

Hazard	Potential Effect(s)	Early Recognition	Mitigation
General anesthesia (procedural)	Aspiration-infection Pulmonary compromise-ARDS Urinary retention, suprapubic catheterization Paralysis Coma Death	Periodic assessment of airway patency, respiratory rate, and oxygen saturation. Routine monitoring of vital signs	Supervision by trained anesthesiologist Intra-operative monitoring Pre-op history and physical exam
Muscle Blockade (procedural)	Extended anesthesia (too much blockade) Insufficient anesthesia—pain Toxicity (If the organ that metabolizes the muscle block has compromised function)	Physical assessment and pharmacological management per ASA Standards	Pre-op history and physical exam Selection of appropriate agents. Patient management by Anesthesiologist.
Cardiac Arrhythmia (both procedural and device, unlikely from device due to distance)	Acute decrease in BP Fibrillation Cardioversion Death	The Anesthesiologist will be monitoring the patient continuously during procedure.	Anesthesia monitoring History and physical exam Availability of treatment drugs and cardioversion equipment; ECG monitoring and procedure pacing
Multiple Prostate Biopsies (procedural)	Bleeding Infection Hematoma Pain	Needle placement is performed using continuous image guidance.	Biopsy technique and physician training
IRE electrode needles placed in or through sensitive structures. (Foreseeable misuse)	Sharp trauma / perforation of structures. (Blood vessels, nerves, urethra, bowel, bladder). Bleeding Infection. Pain	Probe placement is performed using continuous image guidance. Patients will be monitored for hemodynamic instability	Physician training; product labeling

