10.3 Adverse Device Effects (ADEs) and Unanticipated Adverse Device Effects (UADE) Definition

Adverse device effects (ADEs) are a subset of adverse events (AEs). The ADEs are only those AEs caused by or related to the NanoKnife System. This definition includes any event resulting from insufficiencies or inadequacies in instructions for use, the deployment, or any malfunction of the device, including any event that is a result of a use error or intentional misuse.

An unanticipated adverse device effect (UADE) is any serious adverse effect on health or safety, any life-threatening problem or death caused by, or associated with a device, if that effect, problem, or death was not previously identified in nature, severity, or degree of incidence in the application; or any other unanticipated serious problem associated with a device that relates to the rights, safety, or welfare of subjects.

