12.8.1 Adverse Events

All AEs reported by the sites will be recorded in the EDC. All AEs that meet the criteria for adjudication will be reviewed by the adjudication committee. For the events that are adjudicated, the adjudicated data will serve as the primary data source for analysis purposes. The site-reported AE data will be used for analysis of AEs that do not meet the criteria for adjudication.

A summary of all AEs will be presented, including the number of events and number and percentage of subjects reporting adverse events in the following categories: any AE (including 95% CI for the proportion), any severe AE, any ADE, any AE leading to death, any SAE, and any AE leading to study discontinuation.

A

A breakdown of the number of events and the number and percentage of subjects reporting each AE, categorized by body system and preferred term coded according to the MedDRA dictionary, will be presented. Note that the counting of subjects with each event will be by subject rather than by event so that subjects are only counted once within each body system or preferred term.

A further tabulation of these data, categorized by relationship to NanoKnife System treatment, will be presented. When counting the number of subjects with each event, subjects with multiple events within a particular body system or preferred term will be counted under the category of their most procedure-related event within that body system or preferred term. Relationship to NanoKnife System treatment is categorized as: i) not related (“The cause of the AE is known and is not related to any aspect of study participation including the underlying condition”), ii) reasonably possibly related (“There is a reasonable possibility that the event may have been caused by study participation. The AE has a timely relationship to the study procedure(s); however, it follows no known pattern of response and an alternative cause seems more likely or there is significant uncertainty”), iii) probably related (“It is probable that the event was caused by study participation. The AE has a timely relationship to the study procedure(s) and follows a known pattern of response, but a potential alternative cause may be present.”), iv) definitely related (“The event was definitely related to study participation. A related event has a strong temporal relationship and an alternative cause is unlikely.”), or v) unknown as recorded on the CRF.

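### The SAP tabulates relationship to NanoKnife treatment with definitions that grade relationship to study participation, so biopsy complications can be counted as NanoKnife-related and the related outputs have no stated cut-off

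*Combined protocol and SAP*

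**What the plan says.** **Protocol 5.6** makes the investigator responsible for causality and names two targets, the study procedure and the study device. Table 5-1, directly below, then defines four grades in terms of study participation. Its lowest grade reads: "The cause of the AE is known and is not related to any aspect of study participation including the underlying condition".

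**SAP 12.8.1** reproduces these definitions under a different label: "Relationship to NanoKnife System treatment is categorized as: i) not related", and so on. The top grade is defined as "The event was definitely related to study participation. A related event has a strong temporal relationship and an alternative cause is unlikely". The possibly-related grade includes events where "it follows no known pattern of response and an alternative cause seems more likely or there is significant uncertainty". A fifth grade, absent from Table 5-1, closes the list: "or v) unknown as recorded on the CRF". A subject with several events in one body system or preferred term is counted under the most procedure-related of them.

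**SAP 12.8.2** tabulates SAEs related to NanoKnife System treatment, and 12.8.1 lists related AEs that led to discontinuation. Neither says which of the five grades qualify.

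**Biopsy** is a protocol activity after treatment. It is scheduled at 12 months (Table 4-4). It is also done earlier for a PI-RADS 3 or higher lesion at 3 months, biochemical progression or clinical suspicion (Protocol 4.6.16). The hazard list in Protocol 8.7 (Table 8-1) has an entry headed "Multiple Prostate Biopsies (procedural", with bleeding, infection, hematoma and pain as effects. A separate entry covers rectal tear or perforation from ultrasound-guided biopsy.

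**The concern.** The column heading and the definitions beneath it ask different questions. Taking part in this study means having the ablation, but also biopsies, MRI scans and blood draws. A rater who follows the definitions must grade a clear biopsy complication as related. A rater who follows the heading would grade the same event as not related to NanoKnife treatment. With up to 20 sites, both readings are likely to be used.

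The procedural and post-procedural safety profile is a primary objective. In a single-arm study there is no control group to show how many events come from biopsy or from the disease, so attribution is the main means of separating those from ablation harm. If the scale mixes them, the relatedness table, the treatment-related SAE table and the listing of related discontinuations cannot be read as statements about the device.

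**Working it through.** The plan gives no figure on this point, so the first check is a comparison of the texts.

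**1. Target of the rating**

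| Place | What the event is related to |
|---|---|
| Protocol 5.6, opening text | study procedure, or study device |
| Protocol Table 5-1 | study participation |
| SAP 12.8.1, table label | NanoKnife System treatment |
| SAP 12.8.1, definitions i to iv | study participation, as in Table 5-1 |
| SAP 12.8.1, counting rule | procedure |

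No row of the scale belongs to biopsy or another study test. Table 8-1 marks biopsy as procedural, so even the word procedure does not clearly confine the rating to the ablation.

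**2. A biopsy complication.** Take sepsis soon after an early re-biopsy, with no other likely source. Against the text "The event was definitely related to study participation" the answer is yes. The event then appears as definitely related under a NanoKnife heading and, being serious, in the related-SAE table. The counting rule can extend the effect. A man with bleeding after ablation graded possible, and bleeding under the same preferred term after biopsy graded definite, is counted once, as definite.

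**3. An unexplained event.** Not related requires a known cause, so this grade is closed. On Table 5-1 only the related grades remain, and the possibly-related wording admits significant uncertainty. On the SAP scale, unknown is also available.

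**4. An event due to the prostate disease.** The not-related definition names the underlying condition among the things the event must be unrelated to. On that natural reading the grade is closed here too.

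**5. Cut-off.** Related could mean definite only, probable and above, possible and above, or any of these plus unknown. The SAP names none.

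**6. Size, on assumed rates.** Let t be the share of subjects with a truly NanoKnife-related AE, and b the share with a captured biopsy complication, assumed independent. If the literal definitions are followed, the share shown as related is 1 − (1 − t)(1 − b), and the expected number of extra subjects is 118 × b × (1 − t).

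| t | b = 1% | b = 5% | b = 10% |
|---|---|---|---|
| 5% | 1.1 | 5.6 | 11.2 |
| 20% | 0.9 | 4.7 | 9.4 |
| 50% | 0.6 | 3.0 | 5.9 |

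At t = 20% the share shown as related becomes 1 − 0.80 × 0.99 = 20.8%, 1 − 0.80 × 0.95 = 24.0%, or 1 − 0.80 × 0.90 = 28.0%. One misattributed SAE adds 1/118 = 0.8 percentage points to the related-SAE rate. Both t and b are illustrations; the documents supply neither.

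**The case against.** The best defence is that raters may not follow the definitions literally. Protocol 5.6 points them to procedure and device, the relationship choices are to be listed on the eCRF, and that form is not in the public documents. It may already hold separate device and procedure fields. A rater asked about NanoKnife could also treat a recent biopsy as the likely alternative cause. This stands as a limit on certainty: misclassification follows from the text but cannot be shown to occur. It does not remove the defect, because the SAP still tabulates one scale with these definitions.

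Adjudicated data replace site data for adjudicated events (SAP 12.8.1). This helps for some events. However, neither Protocol 5.10 nor SAP 12.8.1 states the criteria for adjudication or gives the committee its own relatedness definitions, and all other events keep the site's rating.

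Capture after the 12-month biopsy is doubtful, since participation ends with that visit (Protocol 8.5) and follow-up stops at 12 months unless an AE is unresolved (6.5). This stands, and it is why the problem lies chiefly with early re-biopsies.

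It can also be said that over-attribution is conservative for a device. That is true of the literal reading, but inconsistent readings across sites leave the direction unknown.

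Three stronger readings are tempting and not supported:

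- A reader might infer that events of unknown cause are necessarily shown as NanoKnife-related. The SAP has a separate unknown grade, so they need not be.
- A reader might infer that the ADE count inherits the fault. The SAP does not derive ADEs from this table and defines them on their own terms: "The ADEs are only those AEs caused by or related to the NanoKnife System".
- A reader might set a misattributed SAE against the 1.6% in the sample size section. That figure is a true event rate at which 100 subjects give over an 80% chance of seeing at least one medically significant AE. Attribution does not enter it.

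**Conclusion.** The point holds in a bounded form. The label in SAP 12.8.1 and the definitions under it disagree. Followed as written, the definitions put biopsy complications among NanoKnife-related events and bar unexplained events, and on the natural reading disease-related ones, from the not-related grade. The two documents also disagree on whether unknown is a grade, and the related outputs lack a cut-off.

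The effect is confined to the relatedness table, the related-SAE table and the listing of related discontinuations. The primary safety endpoint, AE incidence by type and CTCAE severity, has no relatedness component and does not change. On the assumed rates above, the distortion runs from under 1 to about 11 subjects of 118. That range rests on independence, on the complications being captured, and on raters following the definitions rather than the label. It is worth correcting because it is a stated rule that misattributes harm, not merely a missing detail.

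**What to change.** In Protocol Table 5-1 and SAP 12.8.1:

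- Replace study participation with the NanoKnife device or ablation procedure as the target of the rating.
- Give events due to a study biopsy or other study test their own category, shown apart from NanoKnife-related events. Use existing eCRF fields where they allow it.
- Define not related as no reasonable possibility that the device or ablation procedure caused the event, without requiring a known cause and without reference to the underlying condition.
- Either add unknown to Table 5-1 or remove it from the SAP.
- State which grades count as related in the related-SAE table and the discontinuation listing, and whether unknown is among them.

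For events already entered, query those rated related with onset after a study biopsy, and complete this before database lock.

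The cost is revised wording in both documents and modest re-rating work at the sites. Whether the eCRF must change depends on a form that is not shown. No endpoint, sample size or total AE count changes.

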12.8.2 Deaths and Serious Adverse Events

Serious adverse events (SAEs) and NanoKnife System treatment-related SAEs will be summarized separately by body system and preferred term for the ITT subjects. All SAEs recorded on the CRF will be provided in a listing for subjects in the ITT population.

A table presenting the number of events and the number and percentage of subjects by body system and preferred term who experienced SAEs related to NanoKnife System treatment during the study will be presented for the ITT population. UADEs and deaths occurring in the study will also be listed for all subjects in the ITT population.

12.8.3 Laboratory Data

Blood samples will be drawn for complete blood count (CBC) and for coagulation tests ([Table 17](#)). Hematology and coagulation values are only collected at baseline. Laboratory baseline values for blood samples will be summarized using descriptive statistics for all subjects in the ITT population-

Table 17 Laboratory Tests for Hematology and Coagulation Parameters

Laboratory test	SI Units	Laboratory test	SI Units
Red Blood Cells (RBC, erythrocytes)	10 ¹² /L	Neutrophils (Differential)	%
Hematocrit	fraction of 1	Lymphocytes (Differential)	%
Hemoglobin	g/L	Monocytes (Differential)	%
Erythrocytes MCH	pg	Eosinophils (Differential)	%
Erythrocytes MCHC	g/L	Basophils (Differential)	%
Erythrocytes MCV	fL	Activated Partial Thromboplastin Time (aPTT)	s
White Blood Cells (WBC, leukocytes)	10 ⁹ /L	Prothrombin Time (PT)	s
Platelets	10 ⁹ /L	Prothrombin International Normalized Ratio (INR)	a

a, adimensional; MCH, Mean Corpuscular Hemoglobin; MCHC, Mean Corpuscular Hemoglobin Concentration; MCV, Mean Corpuscular Volume; SI, International System of Units.

Urine samples will be collected at baseline and during study follow-up if there is any question of an active urinary tract infection.

Laboratory tests for urinalysis will be: Specimen Appearance, Color, Specific Gravity, pH, Protein, Glucose, Occult Blood, Ketones, Nitrate, Bilirubin, Leukocyte Esterase, Microscopic Findings: RBC, Microscopic Findings: WBC, Microscopic Findings: Bacteria/Yeast, Microscopic Findings: Casts, Microscopic Findings: Epithelial Cells, Microscopic Findings: Crystals. Laboratory values for urinalysis will be summarized using the frequencies (number and %) of subjects with normal, abnormal but not clinically significant, and abnormal and clinically significant at each timepoint.

Shift tables of the worst-case post-baseline value will be presented by reference range (i.e., normal, abnormal but not clinically significant, and abnormal and clinically significant) for urinalysis. Shift tables will include all urinalysis assessments.

12.8.4 Vital Signs

Values and change from baseline in vital signs will be summarized by time point for all subjects in the ITT population. Descriptive statistics will be presented. Parameters include height (only at baseline, in cm),

weight (kg), body mass index (BMI, kg/m²), temperature (°C), systolic and diastolic blood pressure (mmHg), respiration rate (breaths/min), and pulse (beats/min).

12.8.5 Physical Examinations

Results of physical examinations will be summarized by time point for all subjects in the ITT population. A tabulation of the number and percentage with each possible result will be presented for applicable body systems. Parameters include a standard physical exam by body system to assess if all is normal, and if not if clinically significant.

14.0 Glossary of Abbreviations

Glossary of Abbreviations:	
ADE	Adverse Device Effects
AE	Adverse Event
AJCC	American Joint Committee on Cancer
aPTT	activated Partial Thromboplastin Time
ATC	Anatomic Therapeutic Classification
BMI	Body Mass Index
CBC	Complete Blood Count
CI	Confidence Interval
CRF	Case Report Form
CTCAE	Common Terminology Criteria for Adverse Events
eCRF	electronic Case Report Form
EQ-5D	5-Dimension scale EuroQoL
EPE	ExtraProstatic Extension
ESUR	European Society of Urogenital Radiology
HIFU	High-Intensity Focused Ultrasound
HRQoL	Health-Related Quality of Life
IIEF-15	15-item International Index of Erectile Function
INR	International Normalized Ratio (of Prothrombin)
IPSS	International Prostate Symptom Scores
IRE	IRreversible Electroporation
ITT	Intention-To-Treat
LOCF	Last Observation Carried Forward
MCH	Mean Corpuscular Hemoglobin
MCHC	Mean Corpuscular Hemoglobin Concentration
MCV	Mean Corpuscular Volume
MedDRA	Medical Dictionary for Regulatory Activities
mpMRI	multiparametric Magnetic Resonance Imaging
MRI	Magnetic Resonance Imaging
PI-RADS	Prostate Imaging-Reporting And Data System
PP	Per Protocol
PSA	Prostate-Specific Antigen
PSO	Predictiv Study Operations
PT	Prothrombin Time

QoL	Quality of Life
RBC	Red Blood Cells
SAE	Serious Adverse Event
SAP	Statistical Analysis Plan
SI	International System of Units
SOC	System Organ Class
SS	Screening Set
TURP	TransURethral Prostatectomy
UADE	Unanticipated adverse device effect
UCLA-EPIC	University of California Los Angeles-Expanded Prostate cancer Index Composite
UTI	Urinary Tract Infection
VAS	Visual Analogue Scale
WBC	White Blood Cells
WHO-Drug	World Health Organization drug dictionary
